5.4.2. BI 836826

BI 836826 is administered intravenously as a rate controlled infusion. Administration will start on Week 2 with an initial of 10 mg on Day 8, 50% of the assigned dose on Days 9 and Day 15, and 100% of the assigned dose on Day 22. Thereafter, 100% of the assigned dose will be administered every 2 weeks through Week 18, and every 4 weeks through Week 46. During the Phase 1b portion of the study, subjects will be hospitalized overnight on Day 9 (first 50% dose) for monitoring and prophylaxis against tumor lysis syndrome (TLS).

In the Phase 1b portion of the study, the initial BLRM will use the following dose levels for BI 836826: 100 mg, 200 mg, and 400 mg; the starting dose level will be 100 mg. The BLRM may subsequently be modified to include additional BI 836826 doses through 600 mg, dependent on safety data from this study and from Boehringer Ingelheim study 1270.1.

Subjects should receive 18 infusions of BI 836826 over the course of the study. There will be no intra-subject dose escalation.

There is no limit on the length of time BI 836826 may be held to allow resolution of toxicity. If both idelalisib and BI 836826 are held during the same period, when appropriate both drugs should be restarted on the same day rather than dosing with idelalisib for 7 days prior to restarting BI 836826. If administration of BI 836826 is delayed by more than 4 weeks, when infusions are restarted pre-medication must be administered for the first 8 weeks. The last BI 836826 infusion must be administered no later than Week 48.

Surveillance of the subject during and until at least 2 hours after the end of the infusion is required for the first 4 BI 836826 infusions (through the first infusion of 100% of the assigned dose). Surveillance should be prolonged as clinically indicated to monitor or treat AEs. Mandatory surveillance can be reduced to at least 1 hour in the fifth and subsequent infusions if no AE occurs during the infusion or the 1 hour surveillance period. Prophylaxis against IRR is required prior to administration (Section 5.8.2.1).

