Grade 3 thrombocytopenia	Maintain current dose and schedule.	Maintain current dose level and schedule; unless associated with significant bleeding, in which case decrease subsequent dose by 50% ³
Grade 4 thrombocytopenia	Required action: During continuing single agent therapy period, withhold for bruising or bleeding until Grade ≤ 3 . Recommended action: During combination therapy period, maintain current dose level. If withheld during continuing therapy period, may resume at same or reduced dose level at investigator discretion ² .	If lasts > 7 days or associated with significant bleeding, decrease subsequent dose by 50% ³ .
Anemia		
Grade ≤ 3	Maintain current dose and schedule.	Maintain current dose level and schedule.
Grade 4	If all other possible etiologies of anemia have been ruled out, idelalisib may be withheld at investigator discretion.	Decrease subsequent dose by 50% ³ .

NCI CTCAE Grade ¹	Idelalisib	BI 836826
NON-HEMATOLOGICAL ADVERSE EVENT		
Rash		
Grade ≤ 2	Maintain current dose and schedule.	Maintain current dose level and schedule.
Grade ≥ 3	Required action: Withhold idelalisib until Grade ≤ 1. Recommended action: May resume at lower dose or discontinue idelalisib at investigator discretion ² .	Delay BI 836826 until Grade ≤ 1. Thereafter, may resume at full dose.
Stevens-Johnson Syndrome/Toxic Epidermal Necrolysis		
Any Grade	Required action: Discontinue idelalisib. Interrupt coadministered medications potentially associated with SJS or TEN. Institute treatment per institutional standards.	Discontinue BI 836826. Institute treatment per institutional standards.
Bowel Perforation		
Any Grade	Discontinue idelalisib.	Discontinue BI 836826.
Diarrhea or Colitis		
Any Grade (in addition see below for response to specific CTCAE grades)	Required action: See Section 5.7.2.1 for required assessments. Recommended action: Ensure good hydration status and provide anti-diarrheal; maintain current dose level. See Section 5.7.2.2 for recommended evaluations.	See below.
Grade ≤ 1	Required action: See Section 5.7.2.1 for required assessments. Recommended action: Provide anti-diarrheal (eg, loperamide) and maintain current idelalisib dose and schedule.	Maintain current dose level and schedule.

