Grade 2 (unless clinical diagnosis is established from medical history and physical examination)	Required action: See Section 5.7.2.1 for required assessments and Section 6.1.8.9 for required testing. Recommended action: See Section 5.7.2.2 for recommended evaluations. Maintain current dose level.	Delay BI 836826 until Grade ≤ 1. Thereafter, may resume at full dose.
Grade ≥ 3 (or persistent Grade 2 diarrhea or colitis without clear etiology)	Required action: Withhold idelalisib. See Section 5.7.2.1 for required assessments and Section 6.1.8.9 for required testing. Consider anti-diarrheal (eg, loperamide) and/or addition of anti-inflammatory agent (eg, sulfasalazine, budesonide). Recommended action: See Section 5.7.2.2 for recommended evaluations. At Grade ≤ 1, may resume at lower dose level ² or discontinue study drug at investigator discretion.	If diarrhea Grade ≥ 3 recurs despite interruption of idelalisib, reduce BI 836826 to 50% ³ . BI 836826 may be increased to 100% upon resolution to Grade ≤ 1 at investigator discretion.

NCI CTCAE Grade ¹	Idelalisib	BI 836826
Hepatic Adverse Events (elevations in ALT, AST)		
Grade ≤1 (ALT/AST ≤ 3 × ULN; Bilirubin ≤ 1.5xULN)	Maintain current dose and schedule.	Maintain current dose level and schedule.
Grade 2 (ALT/AST ≤ 3-5 × ULN; Bilirubin > 1.5- ≤ 3xULN)	Maintain current dose and schedule. Recommended action: Monitor ALT, AST, ALP, and bilirubin at least 1x per week until all abnormalities are Grade ≤ 1.	Delay BI 836826 until Grade ≤ 1. Thereafter resume at full dose.
Grade 3 (ALT/AST > 5-20 × ULN; Bilirubin > 3-10xULN)	Recommended action: Withhold idelalisib. Monitor ALT, AST, alkaline phosphatase (ALP), and bilirubin at least 1x per week until all abnormalities are Grade ≤1. If bilirubin abnormality was Grade <3 resume idelalisib at same dose level. If bilirubin abnormality was Grade ≥3, resume at lower dose level ² .	Withhold BI 836826. Monitor ALT/AST at least 1x per week until Grade ≤ 1. Thereafter, may resume at full dose. If ALT/AST elevation Grade ≥ 3 recurs with BI 836826 at full dose and idelalisib at reduced dose, reduce BI 836826 to 50% ³ . Upon resolution of ALT/AST to Grade ≤1 BI 836826 may be re-escalated to 100% at investigator discretion.

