Grade 4 (ALT/AST > 20 × ULN; Bilirubin > 10xULN)	Required action: Withhold idelalisib. Monitor ALT, AST, ALP, and bilirubin at least 1x per week until all abnormalities are Grade ≤1. If bilirubin abnormality was Grade 4, discontinue idelalisib. Recommended action: If bilirubin abnormality was Grade <4 resume idelalisib at lower dose level ² .	Withhold BI 836826. Monitor ALT, AST, ALP, and bilirubin at least 1x per week until all abnormalities are Grade ≤1. If bilirubin abnormality was Grade 4, discontinue BI 836826.
Pneumonitis (with new onset or worsening of baseline dyspnea, cough, or hypoxia without obvious infectious cause)		
Grade 1 (asymptomatic)	Required action: Withhold idelalisib until resolution to baseline. May resume at lower dose level or discontinue at investigator discretion.	Maintain current dose level and schedule.
Grade ≥ 2	Required action: Discontinue idelalisib permanently in subjects with any severity of symptomatic pneumonitis and institute therapy as clinically appropriate.	Discontinue BI 836826.
Pneumocystis jirovecii pneumonia (PJP)		
Any Grade	Required action: Discontinue idelalisib.	Discontinue BI 836826.
CMV Infection/Reactivation⁴		
Any Grade	Required action: Interrupt idelalisib upon unequivocal clinical or laboratory evidence of CMV infection. Treat according to established clinical guidelines. If the benefits of resuming idelalisib are judged to outweigh the risks, consider pre-emptive CMV therapy.	Discontinue BI 836826.
Hepatitis B Reactivation		
Any Grade	Required action: Discontinue idelalisib.	Discontinue BI 836826.

NCI CTCAE Grade ¹	Idelalisib	BI 836826
OTHER NONHEMATOLOGICAL ADVERSE EVENTS		
Grade ≤ 2	Maintain current dose level and schedule.	Maintain current dose level and schedule.
Grade ≥ 3	Withhold study drug until Grade ≤ 1. May resume study drug at initial or next lower dose ² or discontinue study drug at investigator discretion.	Withhold study drug until Grade ≤ 1. May resume study drug at initial or at 50% ³ or discontinue study drug at investigator discretion.

1. CTCAE, Version 4.03.
2. If assigned idelalisib dose level is 50 mg BID, dose reduction is not possible and idelalisib should be interrupted.
3. Dose reduction of BI 836826 by 50% may be performed twice. If still not tolerated, BI 836826 should be discontinued.
4. CMV should be diagnosed using clinical or laboratory criteria per established institutional standard

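### Table 5-3 fits only a subject still at 100% of the BI 836826 dose: for one already reduced, the hepatic Grade 2 row restores 100% and the recurrent-diarrhea row gives no cut

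*Protocol*

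**What the plan says.** All of the following is in the BI 836826 column of Table 5-3 (Protocol Section 5.6) unless noted.

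- **Hepatic Grade 2.** Delay until Grade ≤1, then: "Thereafter resume at full dose". There is no *may*.
- **Rash Grade ≥3, diarrhea Grade 2, hepatic Grade 3.** Hold until Grade ≤1, then: "Thereafter, may resume at full dose".
- **Diarrhea Grade ≥3.** If it "recurs despite interruption of idelalisib, reduce BI 836826 to 50" per cent. The cell cites footnote 3 and adds a discretionary way back: "BI 836826 may be increased to 100% upon resolution to Grade" 1 or lower.
- **Hepatic Grade 3, recurrence.** If the rise "recurs with BI 836826 at full dose and idelalisib at reduced dose, reduce BI 836826 to 50" per cent, again citing footnote 3. After resolution, "BI 836826 may be re-escalated to 100% at investigator discretion".
- **Other non-hematological Grade ≥3.** After resolution, resume at the initial dose or at 50% (footnote 3), or discontinue.
- **Cytopenia rows.** The triggering events, such as Grade 4 neutropenia beyond 7 days or Grade 4 anemia, cut the next dose by half. No rule for going back up is given.
- **Footnote 3.** "Dose reduction of BI 836826 by 50% may be performed twice"; if the drug is still not tolerated, it is stopped.

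**The concern.** The rows are written one event at a time, each as if the subject arrived at 100%. Footnote 3 provides for a second reduction, so the protocol itself expects some subjects to be on a reduced dose when a later event occurs. For them two rows give a dose that does not fit their history. The hepatic Grade 2 row would undo a cut made for a cytopenia because an unrelated liver-test rise had resolved. The recurrent-diarrhea row would leave the dose where it was when a reduction is intended.

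Both departures are towards more drug in a subject who has already shown toxicity. The components are known effects of BI 836826: in the CLL monotherapy trial (Protocol Section 1.3.3), drug-related Grade 3 or 4 neutropenia was reported in 14 of 36 subjects, drug-related ALT rises in 4 and AST rises in 5. Not all of those neutropenias would trigger a cut, and how often the full sequence occurs cannot be derived from the documents.

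What is at stake is the dose given, not an estimate. SAP Section 4.2.1 only lists BI 836826 administration, and SAP Section 7.6 drops the evaluation of dose-limiting toxicity.

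**Working it through.** The plan states no figure to reproduce. The check compares wordings and follows the dose path by hand.

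**Step 1: what *full dose* means.** Footnote 1 of Appendix Table 1 calls the Day 22 infusion the first full dose. Section 5.4.2 sets Day 22 at 100% of the assigned dose. The hepatic Grade 3 cell sets *full dose* against 50% and then speaks of going back to 100%. Where Table 5-3 means the dose in use, it speaks of the current dose level. So *full dose* is 100% of the assigned dose.

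**Step 2: the footnote 3 path.** Each cut halves the current dose: 100% × 0.5 = 50%; 50% × 0.5 = 25%; if still not tolerated, discontinue.

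**Step 3: apply the two rows to each starting level.**

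| Dose in use before the event | Hepatic Grade 2, as written | Ratio to dose in use | Recurrent Grade ≥3 diarrhea, *to 50%* | Same event, *by 50%* (footnote 3) |
|---|---|---|---|---|
| 100% | 100% | 1 | 50% | 50% |
| 50% | 100% | 100/50 = 2 | 50% (no cut) | 25% |
| 25% | 100% | 100/25 = 4 | 50% (an increase) | both cuts used; discontinue if not tolerated |

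The first line shows no problem. The divergence begins at the second line.

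**Step 4: the same in mg.** The documents do not state the two subjects' assigned dose. Assuming the 100 mg starting level, a subject previously cut to 50 mg would get 100 mg instead of 50 mg after the hepatic event, and 50 mg instead of 25 mg after recurrent diarrhea. Across the initial model's levels of 100 to 400 mg, the hepatic contrast runs from 100 versus 50 mg to 400 versus 200 mg. The diarrhea contrast runs from 50 versus 25 mg to 200 versus 100 mg. The ratio is 2 throughout.

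**Step 5: the related rows.** The *other* Grade ≥3 row has both features for a subject at 50%: its first option is a return to the initial dose, and its 50% option is no change. The hepatic Grade 3 reduction is triggered only at full dose, so there *to 50%* and *one level* agree; rewording it is for consistency.

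**The case against.** **The rows can be read benignly.** In a row that only delays treatment, resuming at full dose may just mean that this event needs no reduction. At a first cut, *to 50%* and *by 50%* coincide. The diarrhea cell cites footnote 3 and allows a return to 100%, so two separate cuts to 50% with a re-escalation between them would also satisfy *twice*. This stands as far as it goes: the table is silent on already-reduced subjects rather than openly contradictory. But the hepatic instruction is unqualified, and an investigator who follows it literally reaches 100%.

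**Other controls exist.** Section 5.4.2.3 requires an AE and blood-count check before every 100% dose. Section 5.6 sends uncertainty to the medical monitor. Section 5.4 keeps the two subjects at their current dose levels. Section 6.6.1 lets study drug be stopped when continuing is not in the subject's best interest. These lower the risk. None sets the dose for an already-reduced subject, and a subject whose counts have recovered passes the check.

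**Stronger readings to avoid.** A reader might infer that the hepatic row contradicts Section 5.4.2, which states: "There will be no intra-subject dose escalation". It does not. The same section steps every subject up from 10 mg through 50% to 100%, and Table 5-3 expressly permits returns to 100%. The sentence fits a bar on exceeding the assigned dose. A reader might also want discretionary re-escalation limited to reversing the cut made for the same event. That is a clinical preference, not a defect in the text.

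**Conclusion.** The point holds as a wording defect for subjects already reduced. Read literally, the hepatic Grade 2 row restores 100%, and the recurrent-diarrhea row gives no reduction to a subject at 50%. The size is two-fold per affected infusion for a subject at 50%. The reach is at most two subjects in a terminated study, with no prior reduction documented and no estimate affected. Severity is minor.

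This rests on *full dose* meaning 100% of the assigned dose, which the protocol's own usage supports, and on a subject having been cut before the later event, which nothing in the documents shows to have happened.

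A reader might turn the two-fold figure into a cumulative excess over the eight infusions scheduled from Week 18 to Week 46, since both subjects are past Week 16. The documents do not support that. No cut is recorded. Section 5.7.1 places transaminase rises mostly in the first 3 months. For Grade 3 or 4 diarrhea or colitis, Section 5.7.2 gives a median onset of 7.1 months among patients who reported diarrhea or colitis: 7.1 × 30.44 / 7 = 30.9 weeks. That leaves four infusions (Weeks 34, 38, 42, 46), and the row is triggered by recurrence, which comes later still.

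**What to change.** Reword one footnote and the affected cells of Table 5-3:

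- **Footnote 3:** *First reduction: 50% of the assigned dose; second: 25%; if still not tolerated, discontinue.*
- **Diarrhea Grade ≥3, the hepatic Grade 3 reduction, and the 50% option in the other non-hematological Grade ≥3 row:** *reduce one level (footnote 3).*
- **Resume instructions for rash Grade ≥3, diarrhea Grade 2, and hepatic Grades 2 and 3:** *resume at the dose in use before this event*, keeping *may* where it now stands. In the other non-hematological Grade ≥3 row, replace the initial-dose option with the same wording.

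Leave the hepatic Grade 3 trigger and the discretionary re-escalation in the diarrhea and hepatic Grade 3 rows as they are.

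The cost is a minor wording amendment with IRB approval (Section 9.2.1) and no added subjects or procedures. The trade-off is that a subject whose cytopenia has recovered would no longer return to 100% through the resume instructions.

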5.7. Requirements and Recommendations Regarding Specific Adverse Events or Conditions

5.7.1. Transaminase Elevations

Consistent with observations in a dog toxicology study, reversible asymptomatic ALT/AST increases were observed early in the idelalisib program in phase 1 studies (101-02 and 101-07) in subjects with hematologic malignancies. Transaminase elevations generally occurred within 4 to 12 weeks of drug initiation, and resolved spontaneously over a period of 2 to 4 weeks with drug being continued for Grade 1 and 2 elevations and drug withheld for Grade 3 or 4 elevations until resolution. These early observations are consistent with the ongoing experience with idelalisib treatment and transaminase elevations are now well characterized as most frequently asymptomatic, transient and occurring within the first 3 months of treatment.

Grade 1 or 2 elevations commonly resolve despite continued idelalisib treatment and Grade 3 or 4 elevations can be managed by temporarily withholding idelalisib. Successful rechallenge after resolution at either the same or lower dose level of idelalisib has been achieved in the majority of subjects. There has been no evidence of impaired synthetic function. Close monitoring of hepatic laboratory tests during therapy is important to allow for appropriate idelalisib interruption and reinstitution so that subjects may continue with study drug treatment.

Cholangitis manifest as hyperbilirubinemia out of proportion to serum transaminase elevations has been observed. While disease-related factors, neutropenia, toxicity from prior therapies, effects of ongoing supportive care, or pre-existing cholelithiasis may have initiated such events, it is possible that idelalisib played a contributory role. In such subjects, rechallenge with idelalisib has been possible and has not been associated with other severe adverse events.

In selected subjects who experience more complicated hepatic AEs, further workup may be warranted particularly in subjects who first experience a serum ALT/AST elevation ≥12 weeks from the start of study drug therapy, who have an elevation in serum bilirubin concentration or coagulation parameters, or who have other characteristics that suggest an atypical change in transaminase values. Hepatic AEs that require additional workup should be discussed with the Gilead Sciences Medical Monitor.

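### Table 5-3, Grade 3 hepatic row: BI 836826 may resume and re-escalate on ALT/AST recovery alone, although the row also covers bilirubin >3-10 x ULN

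*Protocol*

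**What the plan says.** The hepatic block of Table 5-3 (Protocol Section 5.6) is headed "Hepatic Adverse Events (elevations in ALT, AST"), yet every graded row in it also carries a bilirubin limit. The Grade 3 row covers ALT/AST >5-20 x ULN and "Bilirubin > 3-10xULN".

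The BI 836826 cell of that row says "Withhold BI 836826. Monitor ALT/AST at least 1x per week until Grade" ≤1, after which full dose is permitted. If Grade ≥3 ALT/AST elevation recurs with BI 836826 at full dose and idelalisib at a reduced dose, BI 836826 drops to 50%. It may return to 100%, at the investigator's discretion, once ALT/AST is Grade ≤1. The cell mentions neither bilirubin nor ALP.

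The neighbouring cells differ:

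- **Grade 2, BI 836826:** delay until Grade ≤1, no analyte named, then "Thereafter resume at full dose".
- **Grade 4, BI 836826:** "Withhold BI 836826. Monitor ALT, AST, ALP, and bilirubin at least 1x per week until all abnormalities are Grade" ≤1, with discontinuation if bilirubin itself was Grade 4.
- **Grade 3, idelalisib (a recommended action):** withhold, then "Monitor ALT, AST, alkaline phosphatase (ALP), and bilirubin at least 1x per week until all abnormalities are Grade" ≤1, with a lower resume dose if bilirubin was Grade ≥3.

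**The concern.** Bilirubin helps to define entry to the Grade 3 row but is absent from the stated exit test for BI 836826. For a Grade 3 event driven by bilirubin alone, the cell says to withhold while its own resume test is already met. The milder and the more severe BI 836826 cells do not have this gap.

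The pattern is foreseeable. Section 5.7.1 states: "Cholangitis manifest as hyperbilirubinemia out of proportion to serum transaminase elevations has been observed". It allows that idelalisib may have contributed. In such a case ALT/AST could reach Grade ≤1 before bilirubin does. Two sites with the same laboratory values could then decide differently on whether to infuse.

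**Working it through.** There is no plan figure to reproduce. The check is a comparison of cells, followed by a search for any other bilirubin condition on resuming BI 836826.

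**Step 1. BI 836826 cells side by side (Table 5-3).**

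| Row | Bilirubin range in row | Stated recovery test for BI 836826 |
|---|---|---|
| Grade 2 | >1.5 to ≤3 x ULN | Grade ≤1, no analyte named; the Grade ≤1 row includes bilirubin ≤1.5 x ULN |
| Grade 3 | >3-10 x ULN | ALT/AST Grade ≤1 only |
| Grade 4 | >10 x ULN | ALT, AST, ALP and bilirubin all Grade ≤1 |

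**Step 2. Highest bilirubin at which BI 836826 could resume, by reading.**

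- Grade 3 cell taken alone: up to 10 x ULN, because Grade 4 starts above that.
- Hold lasts while the Grade 3 definition (>3) is still met: up to 3 x ULN.
- Grade 2 delay (>1.5 to ≤3) then also applies: up to 1.5 x ULN.

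These are bounds read from the table, not risk estimates. The documents give no rate of Grade 3 bilirubin on the combination.

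**Step 3. Other places that could supply a bilirubin condition.**

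- Section 5.4.2.3 (check before each 100% dose) sets neutrophil and platelet limits and requires acceptable tolerability by reference to Table 5-3. It has no bilirubin limit of its own.
- Section 5.6 text sends uncertain cases to the medical monitor and, where appropriate, favours restarting both drugs on the same day if both were held. It gives no threshold.
- Section 5.7.1 lists raised bilirubin among reasons for possible further workup, with medical monitor discussion if workup is needed. It gives no threshold.
- Section 5.5 exempts Grade 3 ALT/AST elevation from the DLT definition but does not exempt bilirubin by name (laboratory abnormalities attributed to underlying disease are exempt generally). So the DLT rules do not treat bilirubin as the lesser signal.

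**Step 4. Reach.** Section 5.4.2 gives infusions on Days 8, 9, 15 and 22 (4), every 2 weeks in Weeks 6-18 (7) and every 4 weeks in Weeks 22-46 (7): 4 + 7 + 7 = 18, which matches the planned number. Appendix 2, footnote 4, places the subjects past Week 16. The infusions left are at most Week 18 plus Weeks 22, 26, 30, 34, 38, 42 and 46: 1 + 7 = 8 per subject, or 2 x 8 = 16 in all. Only those falling around a Grade 3 hepatic hold could be affected.

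**The case against.** The strongest reply is that the table already prevents the problem. Section 5.4.2.3 requires a fresh look at Table 5-3 before every full dose. Bilirubin above 3 x ULN still meets a row that says to withhold, and bilirubin above 1.5 x ULN meets a row that says to delay. Section 5.6 adds the medical monitor and same-day restart. If a site follows the recommended idelalisib action, same-day restart brings bilirubin in through the idelalisib cell. This largely stands: 1.5 x ULN is the natural ceiling on a whole-table reading. A reader might infer that the protocol authorises infusion at bilirubin up to 10 x ULN. That requires ignoring the row definitions, and the documents do not support it as the intended rule. What remains is that a site must assemble the 1.5 limit by inference, against a cell that states a different test.

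A reader might also infer that all other hepatic cells share one rule from which this cell departs. They do not. The idelalisib Grade 2 cell has no hold, the BI 836826 Grade 2 cell names no analyte, and the BI 836826 Grade 4 cell has no resume sentence.

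The ALT/AST test may be deliberate. Section 5.6 describes its actions as drug-specific, and Section 1.3.3 reports that ALT/AST rises on BI 836826 alone came without bilirubin elevation, with Grade 3 ALT in 1 of 36 subjects (2.8%). That may explain the wording, but it is monotherapy experience. The block heading could also send an isolated bilirubin rise to the other nonhematological row, which at Grade ≥3 withholds to Grade ≤1 and then says "May resume study drug at initial or at 50"%. That sits badly with the bilirubin limits printed in every hepatic row.

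Finally, Section 5.7.1 places most transaminase elevations in the first 3 months, which both subjects have passed; it gives no timing for the cholangitis pattern. With only 2 subjects enrolled and at least 3 evaluable subjects per cohort, both were presumably on idelalisib 50 mg BID (an inference). No lower level then exists and idelalisib would be interrupted; if it were stopped permanently during combination treatment, BI 836826 should stop too. Both facts reduce the reach further.

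**Conclusion.** The concern holds as an inconsistency in one cell: after a Grade 3 hepatic event, resumption and re-escalation of BI 836826 are tied to ALT/AST alone in a row that also includes bilirubin, and no other text states a bilirubin condition. The wording difference is certain. That it would change a dosing decision is much less so, given the whole-table reading.

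Severity is minor. Enrollment is closed, the ceiling is 8 scheduled infusions for each of 2 subjects, bilirubin is in the chemistry panel drawn before each infusion (Section 6.1.8.1, Table 6-1), and under SAP Section 7.7 safety data are only listed. The rule is still live, because Section 5.4 lets both subjects continue at their current doses. The infusion count assumes neither subject had gone beyond Week 16 by more than the footnote implies; if they had, fewer infusions remain.

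**What to change.** In the Grade 3 hepatic row, BI 836826 column:

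- Replace the opening with the Grade 4 cell's instruction to withhold and to monitor ALT, AST, ALP and bilirubin weekly until all are Grade ≤1, or at baseline for subjects admitted with bilirubin raised by Gilbert's syndrome or hemolysis (inclusion criterion 8 admits them). Keep the permission to resume at full dose.
- Make re-escalation to 100% depend on resolution of all abnormalities to Grade ≤1.
- Leave the trigger for the 50% reduction as it is.

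Apply the same baseline allowance to the Grade 2 and Grade 4 BI 836826 cells so that the three agree. If ALT/AST-only recovery is intended for BI 836826, the cell should say so and state what bilirubin is acceptable.

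The cost is a small edit to one table, with IRB/IEC approval (Section 9.2.1). No new assay is needed, since ALP and total bilirubin are on the chemistry panel in Table 6-1. The downside is a possibly longer hold. Section 5.4.2.3 lets skipped doses be made up at intervals of at least 2 weeks, with the last no later than Week 48, so a hold loses an infusion only if no slot is left by then.
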